5.2.3. Prior/Concurrent clinical study experience

- Concurrently participating in another clinical study, at any time during the study period, in which the participant has been or will be exposed to an investigational or a non-investigational intervention (drug/invasive medical device).

5.2.4. Other exclusions

- Pregnant or lactating female.
- Female planning to become pregnant or planning to discontinue contraceptive precautions.
- History of /current chronic alcohol abuse and/or drug abuse as determined by the investigator.
- Any study personnel or immediate dependents, family, or household member.
- **Phase II (Formulation and Schedule-finding):** Child in care. Please refer to the [Glossary of terms](#) for the definition of child in care.

5.3. Lifestyle considerations

Not applicable.

5.4. Screen failures

In the event that the individual is determined ineligible for study participation, he/she is considered a screen failure. A screen failure is an individual who consents to participate in this study but is not entered in the study/ randomised to a study intervention.

The reason for screen failure must be documented in the Screening log. If the individual is determined to be eligible for the study, he/she will be enrolled into the study.

5.5. Criteria for temporarily delaying enrolment/ randomisation/ study intervention administration/blood sampling

(Amended 22 March 2022)

Enrolment/randomisation/study intervention/blood sampling administration may be postponed within the permitted time interval until transient conditions cited below are resolved:

- Acute disease and/or fever at the time of enrolment and/or study intervention administration. Refer to the SoA for definition of fever and preferred location for measuring temperature in this study.
- Participants with a minor illness (such as mild diarrhoea, mild upper respiratory infection) without fever may be enrolled and/or dosed at the discretion of the investigator.
- Significant acute illness within the previous 7 days *of study intervention administration.*
- Receipt of systemic antibiotics within 3 days prior to blood sampling visit (this will defer blood draw).

- A positive test for current infection with COVID-19 *prior to intervention administration*. The testing should have been done using a molecular (polymerase chain reaction [PCR] or antigen test) approved by the country regulatory authorities.
- Participants with known COVID-19 positive contacts *and considered at risk of having contracted a COVID-19 infection according to local regulations*.
- Individuals who have received any other vaccines within 7 days (for inactivated vaccines) or 14 days (for live vaccines) prior to and following each vaccination up to Visit 3 for Phase I, up to Visit 4 for Phase II (Formulation and Schedule-finding) and up to Visit 2 for Phase II (Sourcing)*.

* In case an emergency mass vaccination for an unforeseen public health threat (e.g.: a pandemic) is organised by the public health authorities, outside the routine immunisation program, the time period described above can be reduced if necessary for that vaccine provided it is licensed and used according to the local governmental recommendations and that the Sponsor notified accordingly.

In case of seasonal influenza vaccination, the time period described above can be reduced if necessary, for that vaccine, provided it is licensed and used according to its Prescribing Information and according to the local governmental recommendations.

Under such circumstances, a participant may be considered eligible for study enrolment and randomisation and vaccination and/or blood sampling after the appropriate window for delay has passed and inclusion/exclusion criteria have been re-checked, and if the participant is confirmed to be eligible.

6. STUDY INTERVENTION AND CONCOMITANT THERAPY

Refer to the [Glossary of terms](#) for the definition of study intervention.

6.1. Study intervention(s) administered

Refer to Section 4 for the study intervention administration schedule.

Table 15 Study intervention administered – Phase I

Study intervention name: Study intervention formulation†				Placebo Sodium chloride (NaCl) (0.9%); Water for injections
Dose Form/ Presentation				Solution for injection /Syringe
Product category	Combination	Combination	Combination	Combination
No of doses	2	-	2	-
	-	-	-	2
	-	-	-	2
Volume to be administered^				
Type	Study	Study	Control	
Route of administration	Intramuscular use	Intramuscular use	Intramuscular use	

CONFIDENTIAL212458 (MENACWY=CCI -001 PRI)
Protocol Amendment 4 Final

Study intervention name:	C		Placebo
Administration site			
• Location	Deltoid	Deltoid	Deltoid
• Laterality**	Non-dominant	Non-dominant	Non-dominant
Packaging, labelling and TM:	Refer to SPM for details		
Manufacturer:	GSK	GSK	GSK

† The composition per dose is presented here

CCI

Table 16 Study intervention administered – Phase II (Formulation and Schedule-finding)

Study intervention			Bexsero	Menveo*	Placebo (saline)
Formulation†					Sodium chloride (NaCl) (0.9%); Water for injections
Dose Form/ Presentation					Solution for injection/ Syringe
Product category	Combination	Combination	Combination	Biological	Combination
Control	-	-	2	1	1
Volume to be	CCI [REDACTED]				

CONFIDENTIAL

212458 (MENACWY=CCI -001 PRI)
Protocol Amendment 4 Final

Study intervention administered [†]	C		Bexsero	Menveo*	Placebo (saline)
Type	Study	Study	Control	Control	Concomitant
Route of administration	Intramuscular use	Intramuscular use	Intramuscular use	Intramuscular use	Intramuscular use
Administration site					
Location	Deltoid	Deltoid	Deltoid	Deltoid	Deltoid
Laterality***	Non-dominant***	Non-dominant***	Non-dominant***	Dominant	Non-dominant***
Packaging, labelling and TM:	Refer to SPM for details				
Manufacturer:	GSK	GSK	GSK	GSK	GSK

[†]The composition per dose is presented here.

CCI

Table 17 Study intervention administered – Phase II (Sourcing)

(Amended 22 March 2022)

Study intervention name:	CCI	
Study intervention formulation [†]		
Dose Form/ Presentation		
Product category	Combination	Combination
No of doses		
• CCI	2	-
• CCI	-	2
• CCI	2	-
• CCI	-	2
• CCI	2	-
• CCI	-	2
Volume to be administered [^]	CCI	
Type	Study	Study
Route of administration	Intramuscular use	Intramuscular use
Administration site		
• Location	Deltoid	Deltoid
• Laterality*	Non-dominant	Non-dominant

[figure not shown]
CONFIDENTIAL

212458 (MENACWY=CCI -001 PRI)
Protocol Amendment 4 Final

Study intervention name:	C	
Packaging, labelling and TM:	Refer to SPM for details	
Manufacturer:	GSK	GSK

[†] The composition per dose is presented here

CCI

Study participants must be observed closely for at least 30 minutes after the administration of the study intervention(s). Appropriate medical treatment must be readily available during the observation period in case of anaphylaxis, syncope.

6.2. Preparation/Handling/Storage/Accountability

The study intervention(s) must be stored in a secured place within the temperature range specified on the study intervention's label. The storage temperature should be continuously monitored and recorded with a calibrated (if not validated) temperature monitoring device(s).

Only authorised study personnel should be allowed access to the study intervention(s). Storage conditions will be assessed by a sponsor study contact during pre-study activities. Refer to the SPM for more details on storage and handling of the study intervention(s).

6.3. Measures to minimise bias: randomisation and blinding

6.3.1. Participant identification

Participant identification numbers will be assigned sequentially to the individuals who have consented to participate in the study. Each study centre will be allocated a range of participant identification numbers.

6.3.2. Randomisation to study intervention

There are 2 randomisation processes for each participant in the study:

- Randomisation to study intervention

C

6.3.3. Intervention allocation to the participant

In Phase I and Phase II (Sourcing), the randomisation algorithm will use a minimisation procedure accounting for the study.

In Phase II (Formulation and Schedule-finding), the minimisation procedure will account for age category (10-17 years of age and 18-25 years of age) and previous MenACWY vaccination (priming) (Yes and No)*.

It is recommended to have a balance between age category during enrolment in Phase II (Formulation and Schedule-finding).

Once a participant identification number is allocated, the randomisation system will determine study group and will provide the study intervention number to be used for the first dose. The study intervention number(s) to be used for subsequent dosing will be provided by the same automated Internet-based system (SBIR).

When SBIR is not available, please refer to the SBIR user guide or SPM for specific instructions.

To allow GSK to take advantage of greater rates of recruitment in this multi-centre study and to reduce the overall study recruitment period, an over-randomisation of supplies will be prepared.

Refer to the SPM for additional information about the study intervention number allocation.

Note: * Participants with and without a previous MenACWY vaccination (primed and unprimed).

6.3.4. Allocation of participants to assay subsets

Refer to Section 9 for details on the allocation as per the MenACWY priming and the analysis planned. Blood samples will be collected as detailed in Section 8.1.1.1. Refer to Section 10.2.1 for details on allocation of participants for safety laboratory assays.

Refer to Section 8.1.3 for details on allocation of participants to assay subsets and Section 10.2.2.1.1 for details on randomisation to strains for enc-hSBA testing.

6.3.5. Blinding and unblinding

(Amended 22 March 2022)

6.3.5.1. Phase I and Phase II (Sourcing)

(Amended 22 March 2022)

Data will be collected in an observer-blind manner. To do so, study intervention(s) will be prepared and administered by qualified study personnel who will not participate in data collection, evaluation, review or the entry of any study endpoint (i.e. reactogenicity, safety, efficacy).

Note: Due to the different vaccination schedules in Phase II Sourcing, the study will be observer blind only in terms of the vaccine formulations

The laboratory in charge of sample testing will be blinded to the study intervention assignment. Codes will be used to link the participant and study to each sample. There will be no link between the study intervention and the identity of the participant.

6.3.5.2. Phase II (Formulation and Schedule-finding)

This phase is partially blinded. Data in the 4 ABCWY groups will be collected in an observer-blind manner. To do so, study intervention(s) will be prepared and administered by qualified study personnel who will not participate in data collection, evaluation, review or the entry of any study endpoint (i.e. reactogenicity, safety, efficacy).

Data in the Control group will be collected in an open-label manner i.e. study participants, investigator and site staff personnel will be aware of the treatment administered as 2 study interventions are administered at Visit V1.

The laboratory in charge of the laboratory testing will be blinded to the treatment as well as to the subject number. There will be no link between the study intervention groups and the identity of the participant. In addition, for each sample, a different randomly selected

subject code will be used at each timepoint. This subject coding will prevent the testing laboratory personnel from linking the consecutive timepoints to a specific subject.

Refer to the SPM for additional information about details on study blinding.

6.3.5.3. *Unblinding*

(Amended 22 March 2022)

The participant, the site and sponsor personnel involved in the clinical evaluation of the participants will be unblinded to the treatment assigned at a Phase at completion of that particular Phase.

Refer to Section 4.4 for the definition of study completion per participant.

6.3.5.4. Emergency unblinding

Unblinding a participant's individual study intervention number should occur ONLY in case of a medical emergency when this information is essential for the clinical management or welfare of the participant.

The emergency unblinding process enables the investigator to have unrestricted, immediate and direct access to the participant's individual study intervention via SBIR.

The investigator may contact a GSK Helpdesk (refer to the [Table 18](#)) if he/she needs help to perform the unblinding process (i.e., if the investigator is unable to access the automated Internet-based system).

A physician other than the investigator (e.g. an emergency room physician) or participant/care giver/family member may also request emergency unblinding either via the investigator (preferred option) or via the GSK Helpdesk (back up option). The subject/participant card provides contact information for the investigator, his/her back up and GSK Helpdesk.

Table 18 Contact information for emergency unblinding

GSK Helpdesk
Available 24/24 hours and 7/7 days
The Helpdesk is available by phone, fax and email
[contact]
[contact]
Email: [contact]

Refer to SPM for country-specific numbers

6.3.5.5. Unblinding prior to regulatory reporting of SAEs

GSK policy requires unblinding of any unexpected SAE which is attributable/suspected to be attributable to the study intervention(s), prior to regulatory reporting. Vaccines Clinical Safety and Pharmacovigilance (VCSP) is responsible for unblinding the study intervention assignment within the timeframes defined for expedited reporting of SAEs (refer to the Section 10.3.10.1).

In addition, GSK VCSP staff may unblind the intervention assignment for any participant with a Suspected Unexpected Serious Adverse Reaction (SUSAR) or a SAE that is fatal or life-threatening. For SAEs requiring expedited reporting to 1 or more regulatory agencies, a copy of the report containing participant's intervention assignment may be sent to investigators in accordance with local regulations and/or GSK policy.

6.4. Study intervention compliance

When the study intervention is administered at the site, participants will receive it directly from the investigator or designee, under medical supervision. The date of administration of each study intervention dose in the clinic will be recorded in the source documents.

6.5. Dose modification

Not applicable.

6.6. Continued access to study intervention after the end of the study

(Amended 22 March 2022)

During the study conclusion visit/contact (Telephone T3 in Phase I, Visit V6 in Phase II, Formulation and Schedule-finding and Telephone T2/ **Telephone T3** in Phase II, Sourcing *[as per group allocation]*), the investigator will ask each participant/participant's parent(s)/LAR(s) if they are interested in participating/allowing the participant to join a booster study/long-term study. If a participant/participant's parent(s)/LAR(s) is/are not interested in joining the booster study/long-term study the reason for refusal will be documented, when available, in the participant's eCRF.

The investigator is encouraged to share the immunological assay results of non-responders with the study participants/participants' parent(s)/LAR(s).

It is the responsibility of the investigator to determine the medical care of the non-responder as per local/regional practices, such as re-vaccination.

6.7. Treatment of overdose

Not applicable.

6.8. Concomitant therapy

(Amended 22 March 2022)

At each study visit/contact, the investigator or his/her delegate should question the participant and/or the participant's parent(s)/LAR(s) about all medications/products taken, and vaccinations received by the participant.

The following concomitant medication(s)/product(s)/vaccine(s) must be recorded in the eCRF:

- All concomitant medication associated with an adverse event, including vaccines/products, except vitamins and dietary supplements, administered after the first dose of study intervention (Phase 1 and Phase II, Sourcing: Day 1 to Day 211 **or Day 241 or Day 361 (as per the group allocation)** and Phase II, Formulation and Schedule-finding: Day 1 to Day 541).
- Any concomitant vaccination administered in the period starting 14 days before the first dose of study intervention and ending at the last study contact (Phase 1 and Phase II, Sourcing: -Day 14 to Day 211 **or Day 241 or Day 361 (as per the group allocation)** and Phase II, Formulation and Schedule-finding: Day -14 to Day 541).
- All concomitant medication leading to discontinuation of the study intervention or elimination from the analysis, including products/vaccines. Refer to Sections [5.2.2](#) and [9.3.1](#) for details.
- All concomitant medication which may explain/cause/be used to treat SAE/Adverse Event of Special Interest (AESI) including vaccines/products, as defined in Sections [8.3.1](#) and [10.3.8.2](#). These must also be recorded in the Expedited Adverse Event Report.
- The use of antipyretic and/or other medications to prevent (prophylactic use) and/or treat fever during the first 7 days after vaccination to be recorded in the eCRF.
- The use of analgesics to prevent (prophylactic use) and/or treat pain during the first 7 days after vaccination to be recorded in the eCRF.
- Medications taken for prophylaxis are those intended to prevent the onset of symptoms. Medications taken for treatment are intended to reduce or eliminate the presence of symptoms that are present. An anti-pyretic is considered to be prophylactic when it is given in the absence of fever and any other symptom, to prevent fever from occurring [Refer to [Table 1](#), [Table 3](#) and [Table 5](#) for definition of fever].
- The use of antipyretics and/or analgesic medications within 24 hours prior to vaccination must be identified and the reason for their use (prophylaxis versus treatment) must be described in the source document and Concomitant Medications eCRF.
- The use of systemic antibiotics within 3 days prior to blood sampling visit is a reason to delay blood sampling (see Section [5.5](#), Criteria for temporary Delay of Vaccination).

The Local Medical Lead (LML) should be contacted if there are any questions regarding concomitant or prior therapy.

7. DISCONTINUATION OF STUDY INTERVENTION AND PARTICIPANT DISCONTINUATION/WITHDRAWAL

7.1. Discontinuation of study intervention

‘Discontinuation’ of study intervention refers to any participant who has not received all planned doses of study intervention. A participant who discontinued study intervention may continue other study procedures (e.g. safety or immunogenicity), planned in the study protocol at the discretion of the investigator.

The primary reason for premature discontinuation of the study intervention will be documented on the eCRF as follows:

- Adverse event requiring expedited reporting to GSK
- Unsolicited non-serious adverse event
- Solicited adverse event
- Not willing to be vaccinated
- Other (specify).

7.1.1. Contraindications to subsequent study intervention(s) administration

The eligibility for subsequent study intervention administration must be confirmed before administering any additional dose.

Participants who meet any of the criteria listed below or criteria listed in sections [5.2.1](#) and [5.2.2](#) should not receive additional doses of study intervention. Such participants should be encouraged to continue other study procedures, at the investigators’ discretion (Section [10.3.8.2](#)). All relevant criteria for discontinuation of study intervention administration must be recorded in the eCRF.

- Any occurrence of an event listed in the exclusion criteria which must be always re-assessed by the investigator before administration of the next dose of study vaccine.
- Anaphylaxis following the administration of study intervention(s).
- Participants who experience any SAE judged to be possibly or probably related to study intervention or non-study concomitant vaccine/product, including hypersensitivity reactions.
- Participants who develop any new condition which, in the opinion of the investigator, may pose additional risk to the participant if he/she continues to participate in the study.
- Any condition that in the judgement of the investigator would make intramuscular injection unsafe.

- Occurrence of a new AESI or the exacerbation of an existing AESI that, in the opinion of the investigator, exposes the participant to unacceptable risk from subsequent doses of study intervention. Refer to Section [10.3.5](#) for the definition of AESIs.
- Pregnancy (See Section [10.3.7.1](#)).

7.2. Participant discontinuation/withdrawal from the study

A participant is considered to have withdrawn from the study if no new study procedure has been performed or no new information has been collected for him/her since the date of withdrawal/last contact.

From an analysis perspective, a study ‘withdrawal’ refers to any participant who did not return for the concluding visit/was not available for the concluding contact planned in the protocol.

Investigators will attempt to contact participants who do not return for scheduled visits or follow-up.

All data and samples collected up to and including the date of withdrawal of/last contact with the participant will be included in the study analyses. Refer to [Table 1](#), [Table 3](#) and [Table 5](#) for details.

The primary reason for study withdrawal will be documented in the eCRF, based on the list below. The investigator will document whether the decision to withdraw a participant from the study was made by the participant himself/herself, by the participant’s parent(s)/LAR(s), or by the investigator, as well as which of the following possible reasons was responsible for withdrawal:

- Adverse events requiring expedited reporting to GSK (Refer to Section [10.3.10.1](#) for the details)
- Unsolicited non-serious adverse events
- Solicited adverse event
- Withdrawal by participant, not due to an adverse event*
- Migrated/Moved from the study area
- Lost to follow-up
- Sponsor study termination
- Other (specify)

*If a participant is withdrawn from the study because he/she/the participant’s parent(s)/LAR(s) has withdrawn consent and the reason for withdrawal was provided, the investigator must document this reason in the eCRF.

Participants who are withdrawn from the study because of AEs/SAEs/AESIs/pregnancy must be clearly distinguished from participants who are withdrawn for other reasons.

Investigator will follow participants who are withdrawn from the study due to an AE/SAE/AESI/pregnancy until the event is resolved (see Section [10.3.8.2](#)).

A participant will be withdrawn if the participant's treatment code is unblinded by the investigator or treating physician (Refer to Section [6.3.5.4](#)). The primary reason for discontinuation (the event or condition which led to the unblinding) will be recorded in the eCRF.

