Post-injection assessment (30 minutes)	●				●		●						See Section 10.3.8.1 for more information
Distribution of eDiary	○				○		○						
Review of eDiary		●	●				●‡	●					
Return of eDiary								●					
Recording of solicited AEs (Days 1–7 post-vaccination)	x				x		x						See Section 10.3.8 for more information
Recording of unsolicited AEs (Days 1–30 post-vaccination)	●	●	●		●		●	●					See Section 10.3.8 for more information
Record any concomitant medications/vaccinations	●	●	●	●	●	●	●	●	●	●	●	●	Timeframe for recording of concomitant medications/vaccinations is according to the recording period of the AEs for which they are being administered. See Section 6.8 for more information
Record any intercurrent medical conditions		●	●	●	●	●	●	●	●	●	●	●	See Section 9.3.1 for more information
Recording of any AEs leading to vaccine/study withdrawal, SAEs, pregnancies and AESIs*	●	●	●	●	●	●	●	●	●	●	●	●	See Section 10.3.8 for more information

CONFIDENTIAL

212458 (MENACWY=CCI -001 PRI)
Protocol Amendment 4 Final

Type of contact	Visit	PC	Visit	PC	Visit	PC	Visit	Visit	PC	PC	PC	Visit	Notes
Visit/Phone call no.	V1	T1	V2	T2	V3†	TC††	V4	V5	T3	T4	T5	V6	
Timepoint(s) [refer to Table 4 for visit windows]	Day 1	Day 8	Day 31	Day 91	Day 121	Day 121	Day 181	Day 211	Day 271	Day 361	Day 451	Day 541	
Groups	All	First 45**	All	All	ABCWY groups	Control group	All	All	All	All	All	All	
Recording of SAEs related to study participation, or to a concurrent GSK medication/vaccine	●	●	●	●	●	●	●	●	●	●	●	●	Recording of SAEs related to study participation, or to a concurrent GSK medication/vaccine begins from the time a participant signs the consent form to the study end. See Section 10.3.8 for more information
Study Conclusion												●	Participants who terminate the study early are recommended to complete certain study-related procedures See Section 4.4 and 10.1.9.1 for more information

● is used to indicate a study procedure that requires documentation in the individual eCRF.

○ is used to indicate a study procedure that does not require documentation in the individual eCRF. Documentation will be required in the source documents.

✗ is used to indicate a study procedure that will be documented in eDiary.

^ Procedure to be performed prior to study intervention administration

Abbreviation: PC, phone contact; V, clinic visit; T, telephone call; TC, Telephone call for Control group only; AE, adverse event; SAE, serious adverse event; AESI, adverse events of special interest.

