*** Except SAEs related to study participation or concurrent GSK medication/vaccine, all other safety data will be collected starting from Visit 1 after vaccine administration

The investigator or designee will record and immediately report all SAEs to the sponsor via the Expedited AE Reporting Form. Reporting should, under no circumstances, occur later than 24 hours after the investigator becomes aware of an SAE, as indicated in Section 10.3.10. The investigator will submit any updated SAE data to the sponsor within 24 hours of it being available.

A post-study AE/SAE is defined as any event that occurs outside of the AE/SAE reporting periods defined in Table 34. Investigators are not obligated to actively seek AEs or SAEs from former study participants. However, if the investigator learns of any SAE, including a death, at any time after a participant has been discharged from the study, and he/she considers the event to be reasonably related to the study intervention, the

investigator will promptly notify the study contact for reporting SAEs mentioned in the [Table 40](#).

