10.1.9.1. Study conclusion

(Amended 22 March 2022)

At Phase I conclusion phone call (Day 211), Phase II (Formulation and Schedule-finding) conclusion visit (study conclusion; Visit 6, Day 541) and Phase II (Sourcing) conclusions phone call (Day 211 *in* **██████████ groups, Day 241 in**
██████████ groups and Day 361 in **██████████ groups**), the investigator will:

- Review data collected to ensure accuracy and completeness
- Complete the Study Conclusion screen in the eCRF

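### Protocol 7.2 withdraws a participant from the study after a code-break, which ends planned safety data collection in the blinded arms; the effect is minor and cheap to avoid

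*Protocol*

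**What the plan says.** - **Protocol 7.2** (participant discontinuation/withdrawal from the study) makes withdrawal mandatory when a participant's "treatment code is unblinded by the investigator or treating physician". It then says: "The primary reason for discontinuation (the event or condition which led to the unblinding) will be recorded in the eCRF". The same section counts a participant as withdrawn when no further procedure is done and no further information is collected.
- **Protocol 6.3.5.4** limits emergency unblinding to a medical emergency in which the information is essential for the participant's management or welfare. It does not mention withdrawal or continued follow-up.
- **Protocol 7.1**: "A participant who discontinued study intervention may continue other study procedures", at the investigator's discretion.
- **Protocol 7.1.1** lists anaphylaxis, related SAEs and certain AESIs among the reasons to give no further dose, and adds: "Such participants should be encouraged to continue other study procedures", again at the investigator's discretion.
- **Protocol 8.3.1**: "Investigators are not obligated to actively seek AEs or SAEs from former study participants". It keeps a duty to report "if the investigator learns of any SAE, including a death, at any time after a participant has been discharged from the study", provided the investigator considers the event reasonably related to the study intervention.
- **Protocol Table 11** includes SAEs, AEs leading to withdrawal and AESIs from Day 1 through Day 541 in the F&SF primary safety endpoint.
- **Protocol 6.3.5.2** makes the four ABCWY arms of F&SF observer-blind and the Control arm open-label.

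**The concern.** The emergencies that justify a code-break overlap with the events in 7.1.1: a participant with anaphylaxis or a related SAE may well be unblinded. Under 7.1.1 that participant is to be encouraged to stay in study procedures. Once the code is broken, 7.2 removes the participant from the study.

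Two things are then at stake for the safety data. First, active collection stops, so a later SAE or AESI of a different kind may go unrecorded although it falls within the primary safety endpoint. Second, because the triggering event is recorded as the reason, the rule itself may generate an AE leading to withdrawal, which is another component of that endpoint. In F&SF both effects can in practice arise only in the blinded arms, since there is no code to break in Control. This restriction is inferred from 6.3.5.2; 7.2 does not state it.

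**Working it through.** **1. The rules side by side**

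| | 7.1 / 7.1.1 | 7.2 |
|---|---|---|
| Trigger | Dosing stopped, or an event that stops dosing | Code broken by investigator or treating physician |
| Force | Discretionary: permitted or encouraged | Mandatory, no exception |
| Result | Other study procedures may continue | Withdrawal from the study |

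One participant can meet both triggers. The two rules can still both be followed: without a code-break the discretion applies, and with one the specific rule applies. What remains is that 7.2 defeats the purpose of 7.1.1 in exactly those participants whose event was serious enough to need unblinding.

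**2. Participants exposed in F&SF** (Protocol Table 13)

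206 + 196 + 206 + 196 = 804 of 1000. The other 196 are in Control. One participant is 1/206 = 0.49% or 1/196 = 0.51% of an arm.

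**3. Loss per code-break** (Protocol Table 3, ABCWY schedule, assuming no contact afterwards)

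- *Just after Day 1:* 541 − 1 = 540 days. Remaining contacts are V2, T2, V3, V4, V5, T3, T4, T5 and V6, which is 9, or 10 for the first 45 F&SF participants, who also have T1. Samples at risk for primary or secondary objectives are V2 (Day 31) and V5 (Day 211).
- *Just after Day 121:* 541 − 121 = 420 days. Remaining contacts are V4, V5, T3, T4, T5 and V6, which is 6. The V5 sample is at risk.
- *Just after Day 181:* 541 − 181 = 360 days. Remaining contacts are V5, T3, T4, T5 and V6, which is 5. The V5 sample is at risk.

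The V6 sample serves tertiary objectives only (Table 27 footnote). All ABCWY arms are injected on Day 1, so the first line is the maximum.

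**4. Share of planned follow-up**

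Planned ABCWY person-days: 804 × 540 = 434,160.

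The documents give no code-break rate. I assume 1 to 8 code-breaks, all just after Day 1:

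- 1 × 540 = 540; 540 / 434,160 = 0.12%
- 8 × 540 = 4,320; 4,320 / 434,160 = 1.0%

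For each assumed count this is the most that can be lost.

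**The case against.** The strongest reply is that nothing is inconsistent: 7.2 is a specific mandatory rule, 7.1 and 7.1.1 are discretionary rules on another trigger, and a site can obey all three. That is correct. A reader might infer an outright contradiction, and the documents do not support it. Nor does the word discontinuation in 7.2 blur the outcome, since the section's own heading uses it for leaving the study.

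Safeguards also limit the harm. Data and samples up to withdrawal stay in the analysis (7.2). The event behind the withdrawal is followed until resolved (7.2, 10.3.8.2). Related SAEs that come to light later are still reported (8.3.1). These stand, but none restores active collection of a new and different event.

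A reader might also infer that the rule biases a test of safety against Control. The documents do not show such a test: the safety objective is to evaluate, by frequencies and percentages, and the hypotheses in 9.1.2 concern only enc-hSBA activity and the 4-fold rise. The effect is on descriptive per-arm frequencies. Among the four ABCWY arms the rule applies alike.

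Finally, the added AE leading to withdrawal is possible, not certain. An event that justifies emergency unblinding will often already count as an SAE or AESI, and the safety methods (Protocol 9.4.2, SAP 5.3) are redacted, so the counting rule cannot be checked.

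**Conclusion.** The point holds as a minor design weakness. Mandatory withdrawal after a code-break gives up planned safety follow-up, in F&SF only in the four blinded arms, with little visible gain: Control participants know their vaccine and are followed to Day 541, and the testing laboratory is blinded to treatment and subject number (6.3.5.2).

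The size is at most 540 days, 9 or 10 contacts and two samples per code-break, and at most 0.12% to 1.0% of planned ABCWY person-days for 1 to 8 code-breaks. That count is an assumption. The figures also assume no contact at all after the code-break, so the real loss should be smaller. A reader might take the second-dose period from Day 121 as the worst case (420 days, 6 contacts), but Day 1 is also an injection day and gives the larger loss.

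A reader might further infer damage to the primary immunogenicity objectives. With so few participants likely to be affected, the visible text does not support that. Under 9.3.1, those who meet a 7.1.1 criterion may in any case be eliminated from the per-protocol analysis. The SAP section on analysis sets is redacted, so any handling of code-breaks there cannot be seen.

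**What to change.** Reconcile 7.2 with 7.1 and 7.1.1 by separating study-intervention status from data collection:

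- A code-break alone does not end the already planned safety contacts. Planned blood samples continue at the investigator's discretion and with consent.
- Record the code-break and its date in the eCRF, separately from any withdrawal reason.
- List code-breaks by arm in the study report.

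This makes no statement on further dosing.

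**Cost:** a wording change in 7.2, which needs a protocol amendment with IEC/IRB approval, one eCRF date field and one listing. It adds no visits. If follow-up is already complete, the listing by arm is still worth producing, since it shows whether the rule affected the safety frequencies. The downside is that some later AE assessments in these participants are unblinded, as they already are in Control.
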